9.11. Derivation of the Stratification Factor

The stratification factor will be derived from the Prior and Concomitant Medications DMARD CRF page, and specifically from the biologic DMARD (bDMARD) subcategory. Each of the strata will be derived as follows.

1. bDMARD-naïve: subjects who had no prior exposure to any bDMARD prior to Day 1 of the study. This will be checked using the DMARD CRF page where subjects should have no entry on the bDMARD subcategory.
2. TNFi-IR: subjects who had inadequate response to one or at most two different TNFi therapies. For prior use of a given TNFi, an inadequate response is defined in one of the following two possible conditions:
 - a. Discontinued due to adverse event or intolerability: TNFi was taken and was discontinued due to adverse event prior to Day 1 of the study. This will be checked using the Prior and Concomitant Medications DMARD CRF page (bDMARD subcategory) where the start date and end date were before Day 1 of the study and "Adverse Event" was checked under Reason for Discontinuation; or
 - b. Discontinued due to lack of efficacy: TNFi was taken and was discontinued due to lack of efficacy prior to Day 1 of the study. This will be checked using the Prior and Concomitant Medications DMARD CRF page (bDMARD subcategory) where the start date and end date were before Day 1 of the study and "Lack of Efficacy" was checked under Reason for Discontinuation.
3. bDMARD Use (Non-IR): subjects who had prior exposure to any bDMARD (TNFi or non-TNFi bDMARD) prior to Day 1 of the study documented on the DMARD CRF page (bDMARD subcategory).

Subjects in (1) above are grouped to the "bDMARD-naïve" stratum and subjects in (2) and (3) are grouped to the "TNFi-IR or bDMARD Use (Non-IR)" stratum.

Any subjects with three or more TNFi-IR or with non-TNFi bDMARD-IR due to protocol deviation will be included in the stratum of "TNFi-IR or bDMARD Use (Non-IR)" for analysis purpose.

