5.1. Allocation to Treatment

Allocation of subjects to treatment groups will proceed through the use of an interactive response technology (IRT) system (interactive Web-based response [IWR]). The site personnel (study coordinator or specified designee) will be required to enter or select information including but not limited to the user's identification (ID) and password, the protocol number, patient population (bDMARD-naïve or TNFi-IR or bDMARD use [non-IR]) and the subject number. The site personnel will then be provided with a treatment assignment, randomization number, and dispensable unit (DU) or container number when investigational product is being supplied via the IRT system. The IRT system will provide a confirmation report containing the subject number, randomization number, and DU or container number assigned. The confirmation report must be stored in the site's files.

The study-specific IRT reference manual will provide the contact information and further details on the use of the IRT system.

Subjects will be randomized at the Baseline visit in a 1:1 ratio to one of the following two parallel blinded treatment sequences for a total of 16 weeks of treatment. Eligible subjects will be treated with one of the two sequences for 16 weeks followed by treatment with tofacitinib 5 mg BID for an additional 32 weeks.

Randomization will be stratified by prior treatment history: (1) bDMARD-naive and (2) TNFi-IR or bDMARD use (non-IR). During the feasibility phase of clinical trial preparation, the sponsor conducted a survey of the countries and sites likely to participate in the study. While there was country-to-country variability, the overall proportion of bDMARD-naïve and TNFi-IR or bDMARD use (non-IR) was approximately 80%/20% respectively. The clinical trial was thus designed to reflect this prevalence. Subjects with more than 2 TNFi failures were excluded due to the higher likelihood that they could be refractory to tofacitinib therapy, an observation noted in other tofacitinib trials in RA and PsA.

Strata (Patient Population)	Sequence	Treatment Sequence and Description	Planned Number of Randomized Subjects
bDMARD-naive	1	Blinded Tofacitinib 5 mg BID for 16 weeks followed by open-label tofacitinib for 32 weeks One-tofacitinib 5 mg tablet in AM & PM	96

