5.8.1. Biologic Medications

Prior treatment with bDMARDs including TNF inhibitors is permitted if they have been discontinued for at least five half-lives before randomization. See also [Section 4.1](#) for definition of a TNF inhibitor nonresponder. Subjects on bDMARDs including TNF inhibitors must be discontinued according to the following criteria:

- Etanercept (Enbrel®): Discontinued at least 4 weeks prior to the first dose of investigational product;
- Adalimumab (Humira®): Discontinued at least 10 weeks prior to the first dose of investigational product;
- Infliximab (Remicade®): Discontinued at least 8 weeks prior to the first dose of investigational product;
- Golimumab (Simponi®): Discontinued at least 10 weeks prior to the first dose of investigational product;
- Certolizumab (Cimzia®): Discontinued at least 10 weeks prior to the first dose of investigational product;
- Other bDMARDs: Discontinued at least 4 weeks or 5 half-lives (whichever is longer) washout period prior to first dose of study treatment after discussion with Sponsor.

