4.2.2. Deviations Assessed Prior to Randomization

Exceptions to the inclusion or exclusion criteria are not expected to occur; but any subject who fails meeting any of the following protocol inclusion criteria will be excluded from the PP analysis set.

- Subjects who failed to meet the Modified New York Criteria for Ankylosing Spondylitis (1984) at screening. The AS diagnosis at screening is recorded on the Case Report Form (CRF) page for primary diagnosis. A subject who did not have this CRF page filled out will be considered having this exclusion criterion for PP analysis set met.
- Subjects who had BASDAI score <4 or back pain score (BASDAI Question 2) <4 assessed at either screening or Baseline (ie, Day 1) visit. The BASDAI CRF pages at screening and Baseline will be used to check this condition.
- Subject who failed to meet the criteria of at least 2 NSAIDs-IR (see definition of inadequate response to NSAID in [Appendix Section 9.10](#)).
- Subjects who failed to meet the criteria of:
 - Being naïve to prior bDMARD, or
 - Having an inadequate clinical response or intolerance due to treatment-related AE to at least 1, but not more than 2 approved TNFi's (ie, 1 or 2 TNFi-IR) or having bDMARD Use (Non-IR).

[Appendix Section 9.11](#) provides more details on how to check these criteria and to derive the stratification factor.

Full lists of DMARDs and NSAIDs can be found in [Section 9.6](#).

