6.4. Subset (Subgroup) Analyses

6.4.1. Subgroup Analyses for Primary Endpoint of ASAS20 at Week 16

All subgroup comparisons for the primary endpoint ASAS20 at Week 16 will be made on the FAS with missing value handled by MR=NR using the on-drug data corresponding to Estimand 1 for the following comparison only:

- Tofacitinib 5 mg BID vs. Placebo.

Subgroup analysis will be performed for each of the following subgroup variables and their categories in parentheses:

- Prior treatment history - 2 categories ("bDMARD-naïve", "TNFi-IR or bDMARD Use [Non-IR]") where prior treatment history is derived from the clinical database (see [Appendix Section 9.11](#));
- Prior treatment history – 3 categories ("bDMARD-naïve", "TNFi-IR", "bDMARD Use [Non-IR]") where prior treatment history – 3 categories is derived from the clinical database. Subjects under "bDMARD Use (Non-IR)" category are not TNFi-IR and have prior bDMARD Use without IR. This subgroup analysis is only done when there is sufficient number of subjects in the "bDMARD Use (Non-IR)" category (see [Appendix Section 9.11](#));
- Geographic region – 4 regions ("North America (US and Canada)" [United States, Canada], "European Union" [Bulgaria, Czech Republic, France, Hungary, Poland], "Rest of World" [Ukraine, Russia, Australia, Turkey], "Asia" [China, South Korea]);
- Gender (Female, Male);
- Race (White, Asian, Other), when a subject selects more than one race category, this subject will be grouped to the "Other";
- Age at Baseline (<65, \geq 65 years);
- Baseline weight (<60, \geq 60 to \leq 100, >100 kg);

- Baseline Body Mass Index (BMI) (<25, ≥25 to <30, ≥30 to <40, and ≥40 kg/m²);
- AS disease symptom duration (<5, ≥5 years);
- Baseline AS disease activity (ASDAS_{CRP} <1.3 [inactive disease], ≥1.3 to <2.1 [low disease activity], ≥2.1 to ≤3.5 [high disease activity], > 3.5 [very high disease activity] units, and continuous) (van der Heijde et al. 2016; Machodo et al., 2018);⁹
- Baseline hsCRP (≤2.87, >2.87 mg/L), where 2.87 mg/L (the upper limit of normal) is defined in this study as elevated;
- Baseline smoking status (Never Smoked, Former Smoker, Current Smoker);
- Day 1 Concomitant csDMARD Use (Yes, No);
- HLA-B27 (Positive, Negative).

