6.5. Baseline and Other Summaries and Analyses

6.5.1. Baseline Summaries

Baseline characteristics will include but may not be limited to the ones listed below and will be summarized descriptively. For continuous variables, the summary will include N (which is the number of subjects evaluable for the baseline characteristics), mean, median, SD and range (ie, minimum and maximum); for binary and categorical variables, the summary will include frequencies and percentages. A missing category will be included for those subjects with missing value. In addition to displays by treatment groups, the summaries will also be provided for all the treatment groups combined.

Demographic characteristics:

- Baseline age (2 categorizations: <18, ≥18 to ≤44, ≥45 to ≤64, ≥65 years; <18, ≥18 to ≤44, ≥45 to ≤64, ≥65 to ≤74, ≥75 to ≤84, ≥85 years; and continuous in years);
- Gender (Female, Male);
- Race (White, Black, Asian, Other);
- Geographic region (see [Section 6.4.1](#) for definition);
- Ethnicity (Hispanic/Latino, non-Hispanic/Latino);
- Baseline body weight (<60, ≥60 to ≤100, >100 kg; and continuous in kg);
- Baseline height (continuous in cm);
- Baseline waist circumference (continuous in cm);

- Baseline BMI (<18.5, ≥18.5 to <25, ≥25 to <30, ≥30 to <40, and ≥40 kg/m²; and continuous kg/m²);
- Baseline smoking status (Never Smoked, Former Smoker, Current Smoker);
- Duration of smoking started (continuous in years) for subjects who are Current Smokers or Former Smokers;
- Duration of smoking stopped (continuous in years) for subjects who are Former Smokers only;
- Baseline pack-year (continuous in pack-year) for subjects who are Current Smokers or Former Smokers;
- Baseline Alcohol use (Yes, No; continuous in units/week for subjects who have Current Alcohol use at Baseline); Yes is defined for subjects who have Current Alcohol use at Baseline, else No.

Baseline disease characteristics:

- Prior treatment history at randomization ("bDMARD-naïve", "TNFi-IR or bDMARD Use [Non-IR]") where prior treatment history is derived from the clinical database (see [Section 9.11](#)). Under the "TNFi-IR or bDMARD Use (Non-IR)" category, two subcategories: "TNFi-IR" and "bDMARD Use (Non-IR)" will be summarized. Subjects under "bDMARD Use (Non-IR)" are not TNFi-IR and have prior bDMARD Use without IR (see [Section 9.11](#));
- AS disease symptom duration (<5, ≥5 years; and continuous in years);
- AS disease duration since diagnosis (<5, ≥5 years; continuous in years);

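### SAP 9.11 derives bDMARD Use (Non-IR) from exposure alone, contradicting the SAP's other definitions of that category, and calls a deviation something Protocol Section 4 does not forbid

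*SAP*

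**What the plan says.** SAP 9.11 builds the stratification factor from the DMARD page of the CRF. Item 1 is no biologic exposure. Item 2 is inadequate response to one or two TNF inhibitors, judged by the recorded reason for stopping. Item 3 is "bDMARD Use (Non-IR): subjects who had prior exposure to any bDMARD (TNFi or non-TNFi bDMARD) prior to Day 1 of the study", with no reason-for-stopping test. Items 2 and 3 are pooled into one stratum. A closing sentence adds: "Any subjects with three or more TNFi-IR or with non-TNFi bDMARD-IR due to protocol deviation will be included in the stratum", meaning that pooled stratum.

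Elsewhere the SAP describes the third category differently. SAP 6.4.1 says its subjects "category are not TNFi-IR and have prior bDMARD Use without IR". SAP 6.5.1 uses the same definition, and 6.5.2 counts prior biologics for subjects with use but no IR. SAP 3.4.1 defines inadequate response for any medication by its reason for discontinuation.

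SAP 4.2.2 removes from the per-protocol set anyone who is neither naïve, nor a one- or two-TNFi inadequate responder, "or having bDMARD Use (Non-IR)". It sends the reader to 9.11 for how to check this.

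In the protocol, inclusion 8 limits TNFi failures to two. Exclusion 5 covers targeted synthetic DMARD exposure and current biologic use. Protocol 5.8.1 states: "Prior treatment with bDMARDs including TNF inhibitors is permitted if they have been discontinued for at least five half-lives before randomization". Section 3 names only non-IR prior users as eligible beyond the naïve and TNFi-IR groups.

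**The concern.** The rule a programmer would implement lacks the condition that the rest of the SAP assumes. Two programmers working from this text could produce different per-protocol sets and different three-category subgroup tables, each defensibly. The per-protocol analysis supports both the primary and the key secondary endpoint, so its membership should not turn on interpretation.

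Separately, 9.11 presumes an eligibility rule that no numbered criterion states. The protocol defines inadequate response only for NSAIDs and TNF inhibitors (Section 3 and inclusion 7). A site could therefore enter a subject who failed a non-TNFi biologic as a non-IR prior user in good faith. The three-way status confirmation in Protocol 6.2.1 does not prevent that.

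**Working it through.** **Classification.** The inputs are items 1 to 3 of SAP 9.11 and the fourth exclusion in SAP 4.2.2. Each prior-biologic history is run through them twice: with item 3 as worded (exposure only), and with the without-IR condition of 6.4.1, 6.5.1 and 6.5.2.

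| History | Item 3 as worded | Item 3 with without-IR condition |
|---|---|---|
| No biologic | Item 1; passes | Item 1; passes |
| 1–2 TNFi failures | Items 2 and 3; passes | Item 2; passes |
| Biologic use, no failure | Item 3; passes | Item 3; passes |
| Non-TNFi failure only | Item 3; passes, labelled Non-IR | No category; fails |
| 3 or more TNFi failures | Item 3; passes, labelled Non-IR | No category; fails |
| 1–2 TNFi failures plus a non-TNFi failure | Items 2 and 3; passes | Item 2; passes |

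Three results follow.

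1. As worded, items 1 and 3 cover every possible subject (unexposed or exposed), so the 4.2.2 exclusion has nobody left to exclude.
2. The two readings differ for exactly two histories: non-TNFi failure only, and three or more TNFi failures. On the without-IR reading those subjects fall in no category, so the text does not say where the three-category subgroup and the baseline subcategories report them.
3. The last row passes on both readings through the TNFi-IR limb, although 9.11 treats a non-TNFi failure as a deviation. Adding a without-IR condition to item 3 does not settle that case.

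**Eligibility.** Inclusion 8 is silent on non-TNFi biologics. Exclusion 5 does not reach past use of a biologic. Protocol 5.8.1 permits past use whatever the response. Against these stand Section 3, which names only non-IR prior users, and 9.11, which says "with non-TNFi bDMARD-IR due to protocol deviation will be included in the stratum". These places do not agree.

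**Primary analysis.** The plan's own figure is about 89% power for 40% against 60% with 120 per arm at two-sided 5%. With unpooled variance, as in SAP 5.2.1.1: SE = √(0.4×0.6/120 + 0.6×0.4/120) = 0.0632, and power = Φ(0.20/0.0632 − 1.96) = 88.5%. A pooled-variance calculation gives 87.7%. The stated figure is reproduced. Changing item 3 does not alter it, because 9.11 already puts these subjects in the pooled stratum and they remain in the full analysis set.

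**Illustration only.** Suppose k of the 240 subjects are such failures and get no benefit; the documents give neither figure. The difference becomes 0.20×(1 − k/240), with placebo held at 40%:

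- k = 6: 19.5 points, power 86.9%
- k = 12: 19.0 points, power 85.0%
- k = 24: 18.0 points, power 80.9%

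The pooled stratum is planned at 48 subjects (24 + 24), so k = 24 would be half of it. Any such loss would come from who is enrolled, not from the wording of 9.11.

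**The case against.** The strongest reply is that item 3 should not be read alone. Its own label says Non-IR. SAP 6.4.1, 6.5.1 and 6.5.2 all add the condition, and 3.4.1 supplies a general definition of inadequate response. The closing sentence of 9.11 would be redundant if item 3 already covered those subjects. Read literally, item 3 would also absorb every TNFi-IR subject, which cannot be meant. SAP 4.2.1 further allows deviations to be added before the per-protocol list is finalised.

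Much of this stands. It shows what was probably intended, and it means misclassification is not a settled outcome. It does not remove the contradiction, because 4.2.2, 6.4.1, 6.5.1 and 6.5.2 all refer to 9.11 for the derivation, and the missing condition is there. The closing sentence fixes only the stratum. It is silent on per-protocol membership and on which category reports these subjects.

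A reader might also infer that the patients Protocol 5.1 means to keep out can be enrolled freely. The documents do not support that. The stated reason is "Subjects with more than 2 TNFi failures were excluded due to the higher likelihood that they could be refractory to tofacitinib therapy"; it concerns TNFi failures, and inclusion 8 and Section 3 already set that limit. Extending it to a single non-TNFi failure is inference.

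**Conclusion.** The point holds as an internal contradiction with limited reach. Item 3 of SAP 9.11 conflicts with three other SAP sections. Taken literally, it disables one per-protocol exclusion and labels a non-TNFi failure, or three or more TNFi failures, as Non-IR. SAP 9.11 and the protocol also disagree on whether a prior non-TNFi inadequate responder is eligible.

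The SAP wording affects the supportive per-protocol analyses of ASAS20 and ASAS40, the three-category subgroup (run only if the Non-IR group is large enough, without p-values) and the baseline tables. How many subjects are involved cannot be known from the documents.

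It would be tempting to conclude that the primary result is biased or underpowered. The documents do not support this: the full analysis set and the CMH strata are the same on either reading, and the power losses shown rest on assumed counts and zero benefit. Inadequate response here includes stopping for an adverse event, so zero benefit is not a natural assumption.

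**What to change.** 1. In SAP 9.11 item 3, add that none of the prior biologics was discontinued because of an adverse event or lack of efficacy.
2. Add a category, other bDMARD-IR, for three or more TNFi failures or any non-TNFi biologic failure. Keep it in the pooled stratum for the full analysis set, as 9.11 already directs, and out of the Non-IR subgroup. State its per-protocol handling in 4.2.2, including for subjects who also have one or two TNFi failures, before the Week 16 unblinding.
3. Reconcile Protocol Sections 3, 4 and 5.8.1 with SAP 9.11 on whether a prior non-TNFi biologic inadequate responder is eligible, so that sites and the deviation list apply one rule.

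The reason for discontinuation is already on the DMARD CRF page, so steps 1 and 2 are wording and programming changes only. The cost is possibly a slightly smaller per-protocol set. Sample size, alpha and the primary analysis are untouched.
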